Secondary outcomes will assess bleeding complications (defined as unplanned ED visit/clinicvisit/procedure/admission related to bleeding, clot retention, clot evacuation, need for perioperative transfusion) between patients who receive TXA vs. those do not. We will also assess differences in perioperative complications associated with TXA including but not limited to: deep venous thrombosis, pulmonary embolism, cerebrovascular events, between the groups. We will also assess for the duration of postoperative hematuria between groups. Additionally, we will assess for differences in operative times between the groups.

We anticipate that there may be up to a 25% increase in SDD rates in those who receive TXA vs. those who do not.

BACKGROUND:

Holmium Laser Enucleation of the Prostate (HoLEP) is a size-independent treatment option for benign prostate hypertrophy (BPH) as recommended by the American Urological Association (AUA) Guidelines.¹ Furthermore, HoLEP is one of the few surgical options that is recommended by the AUA for patients on active anticoagulation given its superior hemostatic properties.¹ [name] research team has previously shown that same-day catheter removal and same-day discharge (SDD) was successful in approximately 87% of patients.² This study was performed in a limited cohort of 207 patients. [name] was recently recruited to Northwestern Medicine to introduce HoLEP to Chicago. Our current SDD rate is approximately 60%. Factors limiting discharge are primarily related to the degree of hematuria and patient anxiety.

Tranexamic Acid (TXA) is an indirect fibrinolytic inhibitor and was discovered in the early 1960s.³ Although it was initially only used in women with heavy menstrual blood loss and those with hereditary bleeding disorders, it is now widely used in trauma situations and orthopedic, cardiac, otolaryngologic, and obstetric surgeries as it is cheap, safe, and effective.³ Oral, IV, topical and combined methods of TXA administration also reduced blood loss and risk of transfusion compared to placebo for patients undergoing total hip arthroplasty.⁴ TXA is safe, but high doses of TXA (80-100 mg/kg) or TXA use in those with poor renal function have been associated with an increased risk of seizures.⁵ While there is no clear evidence of increased risk of thromboembolic events⁶, it should be used cautiously in those with a history of embolic events, those on hormonal contraceptives.⁷

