Use of TXA in Urologic literature has been limited. One prospective, randomized controlled trial studied the use of TXA in 40 men undergoing transurethral resection of the prostate (TURP).⁸ The authors found that TXA resulted in significantly less postoperative serum hemoglobin drop, less hemoglobin loss per gram of resected tissue, shorter OR time, and more resected tissue.⁸ In another prospective, randomized controlled trial, the authors randomized 136 men undergoing TURP to receiving TXA or not.⁹ The authors found TXA resulted in reduced operative blood loss, the amount of blood loss per gram of resected tissue, and shorter OR time. Interestingly, TXA did not decrease length of stay or catheter duration.⁹ In one systematic review analyzing the effects of TXA after transurethral resection of the prostate, the authors included nine studies in their meta-analysis and found that TXA reduced intraoperative estimated blood loss as well as the transfusion rate.¹⁰ The use of TXA in percutaneous nephrolithotomy (PCNL) has also been studied. A randomized, double-blinded, placebo-controlled trial enrolled 192 patients with Guy's stone scores III-IV. Patients were given 1g of IV TXA vs. placebo at time of anesthetic induction. The authors found that TXA administration during PCNL resulted in reduced blood transfusion rate, and higher stone free rates in the immediate postoperative period and at 3 months.¹¹

Although HoLEP is one of the few surgical options recommended by the AUA for patients at high risk of bleeding due to its excellent hemostatic properties, for patients undergoing same-day discharge, hematuria is often the rate limiting factor. Currently, no studies have examined the use of TXA during HoLEP. Therefore, we would like to study if the use of TXA during HoLEP will increase our SDD rates.

STUDY ENDPOINTS:

Primary:

- 1) Difference in same-day discharge and same-day catheter removal rates

Secondary:

- 2) Difference in medical events: defined as unplanned ED visit/clinic visit/procedure/admission related to bleeding, clot retention, clot evacuation, need for perioperative transfusion
- 3) Duration of postoperative hematuria
- 4) Difference in operative, enucleation and morcellation times
- 5) Adverse events related to TXA (thrombotic events (DVT, PE, stroke), seizures,

PROCEDURES INVOLVED:

Visit 1 – Screening (Day -45 – Day 0)

- i. Patients will complete:
 - 1) Patient Informed Consent Form,
 - 2) HIPAA form,

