- ii. Investigative site will complete: patient demographics, medical history, Inclusion/Exclusion Criteria
- iii. Randomization and instructions to patients on whether or not to receive TXA

Visit 2 – HoLEP (Day 0)

- iv. Inclusion/Exclusion Criteria to reconfirm eligibility (only if Screening and HoLEP are not on the same day)
- v. Adverse Events secondary to TXA

Catheter Removal (Day 0 or 1)

Assessment of same day discharge and catheter removal rates

Week 1 through resolution of hematuria

The patient will receive a weekly computer generated text from Twilio (secure software integrated to REDCap) asking them to report their hematuria and dysuria after the procedure. It will also ask if they have had any unplanned visits or interventions. This will continue until 12 week post HoLEP survey

Visit 3 – One month follow-up (Day 30)

If patients have already reported resolution of hematuria, they will receive an additional questionnaire 30 days postoperatively to assess for bleeding complications and symptoms.

Visit 4 – Follow-up (12 weeks Post HoLEP)

- vi. Patient will be assessed for BPH symptom related questionnaires in addition to urinary parameters. Will also confirm if there were or were not bleeding or other complications in first 90 days postoperatively.

Early Withdrawal Patients: The investigator will make reasonable attempts to ensure all enrolled patients complete the study.

****If the patient is unable to complete the questionnaires by text, they will be contacted by phone call for questionnaire completion.**

STU#:

The HoLEP procedure is performed in a similar fashion by all surgeons with similar postoperative care plans. Duration of postoperative catheterization is determined by the treating surgeon, with respect to time of surgical case completion, need for inpatient observation, and patient preference. The portions of the case will not be altered regardless of patient being on anticoagulation or not, however the surgeon will not be blinded to the patient's status of anticoagulation therapy, as this knowledge would be paramount in postoperative management if there were complications.

DATA AND SPECIMEN BANKING

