Data will be collected and stored electronically in REDCap. Quality assurance steps will include testing of database including any potential data calculated by command functions within REDCap (ex: age of patient at time of surgery calculated by using patient's date of birth and date of surgery) by study team prior to moving to production mode. The following quality control methods will be used: 1) single entry of data with random checks of accuracy, and 2) extraction and cleaning of data on a monthly basis that will be used for analysis every 3 months until completion of enrollment.

Data will be accessible to only authorized members of the study team. Any presentations on the study or published findings will use only de-identified data.

Data will be stored for 7 years after the end of the study. After this period, electronic data will be deleted.

SHARING RESULTS WITH PARTICIPANTS

Study results will not be shared with participants.

INCLUSION AND EXCLUSION CRITERIA

Inclusion Criteria

- Males 18 -89 undergoing HoLEP
- Willing to sign the Informed Consent Form
- Able to read, understand, and complete patient questionnaires, pain texts, and medication diary.

Exclusion Criteria

- Allergy or hypersensitivity to TXA, history of acute venous or arterial thrombosis, intrinsic risk for thrombosis or thromboembolism, history of thromboembolic disease, hereditary thrombophilia, use of hormonal agents
- Patients having a concurrent ureteroscopy +/- laser lithotripsy, percutaneous nephrolithotomy, or non-urologic surgery at the time of their HoLEP
- Anticipated need for perineal urethrostomy at the time of HoLEP
- Patient not undergoing catheter removal and voiding trial at Northwestern Memorial Hospital

PARTICIPANT POPULATION(S)

Accrual Number:	Category/Group: (Adults/Children Special/Vulnerable Populations)	Consented: Maximum Number to be Consented or Reviewed/Collected/Screened	Enrolled: Number to Complete the Study or Needed
-----------------	---	---	--

STU#:

			to Address the Research Question
Local	0	110	110
Study-wide	0	110	
Total:	0	110	110

RECRUITMENT METHODS

Enrollment into the study will be performed by a qualified research coordinator.

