After the patient completes their pre-surgical enrollment paperwork in the clinic, they will then be met in a private room away from the treating physicians by a qualified research coordinator who will discuss their potential enrollment and complete any research paperwork. Some patients may be approached via telephone with virtual consent.

Therefore, the initiation of enrollment will begin at the time of the office consultation visit. The patient will remain enrolled until she/he has completed the post-procedure follow up clinic/virtual visit at week 12. Data will not be collected beyond when the patient is seen at the postoperative clinic visit. If the patient is unable to have a physical or virtual visit, a text follow-up will be performed.

After consenting, patients will be randomized to one of two groups.

Group 1 (control): Receive intraoperative 1g TXA

Group 2 (experimental): No TXA

Randomization to **Group 1** or **Group 2** will be allocated through REDCap.¹² The stratified randomization list will be created and provided by the study statistician before the start of patient recruitment.

COMPENSATION FOR PARTICIPATION IN RESEARCH ACTIVITIES

Patients will not be compensated for participating in this research.

WITHDRAWAL OF PARTICIPANTS

If a subject wishes to withdraw from the study, he/she may do so by verbal request to the research team. A subject may be withdrawn from the study by a physician-investigator if determined to be in the subject's best interest for medical reasons.

RISKS TO PARTICIPANTS

The risks in this study are no greater than the risks incurred during a HoLEP. AUA and EAU guidelines support HoLEP as a size independent treatment option for BPH.

Common side effects of TXA are nausea, vomiting, diarrhea, and muscle pain.

POTENTIAL BENEFITS TO PARTICIPANTS

Patients in the TXA arm may have higher rates of success with same day discharge and same day catheter removal.

DATA MANAGEMENT AND CONFIDENTIALITY

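### Poor renal function, which the protocol itself links to seizures under TXA, is not covered by any exclusion, named screening item or dose rule

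*Protocol*

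**What the plan says.** BACKGROUND describes the seizure risk in these words: "high doses of TXA (80-100 mg/kg) or TXA use in those with poor renal function have been associated with an increased risk of seizures". Its next sentence turns to thromboembolism and says of TXA that "it should be used cautiously in those with a history of embolic events, those on hormonal contraceptives". STUDY ENDPOINTS, secondary item 5, lists "Adverse events related to TXA (thrombotic events (DVT, PE, stroke), seizures" as a safety outcome.

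The drug-related bullet under Exclusion Criteria begins "Allergy or hypersensitivity to TXA, history of acute venous or arterial thrombosis, intrinsic risk for thrombosis or thromboembolism" and ends with thromboembolic disease, hereditary thrombophilia and hormonal agents. The other exclusions concern concurrent surgery, perineal urethrostomy and the place of the voiding trial. Inclusion is open to men aged 18 to 89 having HoLEP, with no renal threshold.

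Under PROCEDURES INVOLVED, Visit 1 has two relevant items: "Investigative site will complete: patient demographics, medical history, Inclusion/Exclusion Criteria", then "Randomization and instructions to patients on whether or not to receive TXA". Visit 2 adds "Inclusion/Exclusion Criteria to reconfirm eligibility (only if Screening and HoLEP are not on the same day". The treatment for the TXA group, under RECRUITMENT METHODS, is "Receive intraoperative 1g TXA".

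**The concern.** The protocol names a group of men in whom the study drug may carry a seizure risk, treats seizures as relevant enough to record, and then gives the enrolling site no rule for recognising or handling those men. Patient safety is at stake: a man with poor renal function meets every written criterion and can be assigned the full dose.

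The gap matters more because, under RECRUITMENT METHODS, a research coordinator enrols patients in a room apart from the treating physicians. A coordinator works from the written criteria, and a risk factor that is not among them is easily passed over. Eligibility and dosing are set in a protocol and are not normally left to a statistical analysis plan, so the absence of that plan from the review does not explain the gap.

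**Working it through.** The plan states no figure on this point, so the check is mainly a comparison of texts, with one piece of dose arithmetic.

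**Step 1. Is renal function a risk in its own right?** In the BACKGROUND sentence, high dose and poor renal function are joined by an or. The mg/kg range qualifies high dose only. The renal association is stated with no dose threshold.

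**Step 2. Does any provision cover it?**

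| Place in the protocol | What it covers | Renal rule? |
|---|---|---|
| Inclusion Criteria | Age, HoLEP, consent, ability to complete questionnaires | No |
| Exclusion Criteria | Allergy, thrombosis and related risks, hormonal agents, concurrent surgery, urethrostomy, site of voiding trial | No |
| Visit 1 | Consent and HIPAA forms, demographics, medical history, eligibility check, randomisation | No test named |
| Visit 2 | Recheck of the same criteria; TXA adverse events | No |
| RECRUITMENT METHODS | Flat 1 g dose | No adjustment |
| WITHDRAWAL OF PARTICIPANTS | A physician-investigator may withdraw a subject for medical reasons | Discretionary, no renal trigger |

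Nothing in the right-hand column closes the gap.

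**Step 3. How does 1 g compare with the high-dose range?** Inputs: dose 1,000 mg (RECRUITMENT METHODS); lower bound 80 mg/kg (BACKGROUND); body weights of 50 to 120 kg (assumed).

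Dose per kg = 1,000 mg / weight:
- 120 kg: 1,000 / 120 = 8.3 mg/kg, and 8.3 / 80 = about 10% of the lower bound
- 80 kg: 1,000 / 80 = 12.5 mg/kg, and 12.5 / 80 = about 16%
- 50 kg: 1,000 / 50 = 20 mg/kg, and 20 / 80 = 25%

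The high-dose half of the warning therefore does not apply. The renal half is untouched by this arithmetic, since it carries no threshold.

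**Step 4. Can the harm be sized?** That would need the excess seizure risk at 1 g in men with poor renal function, and the share of HoLEP candidates who have it. The document gives neither and does not define poor renal function. No count of exposed men or of seizures is claimed.

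**Step 5. Where would a new criterion act?** Visit 1 may fall up to 45 days before surgery, and randomisation takes place there. The Visit 2 recheck covers all criteria. A renal exclusion added without further wording would thus be applied a second time, after allocation is known.

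**The case against.** The best defence is that the protocol acts on every caution it states. BACKGROUND attaches its advice to be cautious to embolic history and hormonal contraceptives only, and both became exclusions. For renal function it reports an association and asks for no precaution. This stands. A reader might infer that the protocol contradicts itself, but the document does not support that: it omits a rule and breaks none of its own.

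Second, harm is not shown. The dose is a small fraction of the high-dose range, and BACKGROUND cites a randomised trial in kidney-stone surgery of 192 patients that also used 1 g intravenously. This stands too, as a limit on size. A reader might infer that 1 g is dangerous in these men, or that a certain number will be exposed; neither can be derived. Equally, the protocol does not say that the renal risk is absent at 1 g, and it reports neither renal eligibility nor seizure results for the stone-surgery trial.

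Third, safeguards exist: medical history, the Day 0 recheck, withdrawal by a physician and recording of seizures. They narrow the gap without closing it. History may reveal known kidney disease, but no criterion then excludes the man. The recheck covers only the listed criteria, withdrawal is discretionary, and recording comes after the event.

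A reader might also take this as showing that RISKS TO PARTICIPANTS misstates the risk. That is a separate question. The side effects listed there are described as common ones, which BACKGROUND does not say of seizures, and the consent pages are not available to judge disclosure.

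**Conclusion.** The point holds as a modest safety omission that is worth correcting because the correction is cheap. A seizure risk factor that the protocol itself names has no matching exclusion, screening item or dose rule, so men with it are eligible for a flat 1 g of TXA.

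The only size that can be given is the dose: about 10% to 25% of the 80 mg/kg bound, resting on the assumed weights. Excess seizure risk at this dose and the number of affected men remain unknown. A reader might wish to put a loss of enrolment or power on the correction, but that would need a prevalence the document does not give and would have to assume that every excluded man uses up one of the 110 places. The document does not establish either.

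**What to change.** Add one line to Exclusion Criteria for poor renal function, with an eGFR or creatinine cut-off chosen by the investigators. Check it from existing preoperative results before consent and randomisation, and apply it to all candidates alike so that the two groups remain comparable.

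Add one sentence on Day 0: the renal criterion is decided once, before randomisation. If renal function is then found to have worsened, TXA is withheld on safety grounds and the man stays in his randomised group.

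Cost: a small, unknown number of otherwise eligible men are not enrolled. PARTICIPANT POPULATION(S) sets both the maximum to be consented or screened and the number needed at 110. If that cap counts consented men, a check before consent should use few or none of the places. If it counts every man reviewed, the cap would need to rise by the number excluded.

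Withholding TXA on Day 0 slightly dilutes the comparison. With 55 men in the TXA group (110 split equally, assumed) and a 25-point difference (the anticipated 25% read as percentage points), each such man costs about 25 / 55 = 0.45 points if he then has the no-TXA chance of discharge. No new test is needed if preoperative renal results are routinely available, which the protocol does not state and is assumed here.

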STU#:

NCT05082142

Tranexamic Acid to Improve Same-day Discharge Rates After Holmium Laser Enucleation of the Prostate (HoLEP)

10/29/2021

Protocol

STU#:

PROTOCOL TITLE: Tranexamic acid to improve same-day discharge rates after Holmium Laser Enucleation of the Prostate (HoLEP)

PRINCIPAL INVESTIGATOR:

[name]
Department of Urology
[contact]

VERSION DATE:

10.29.2021

STUDY SUMMARY:

Investigational Agent(s) (Drugs or Devices)	Tranexamic acid
IND / IDE / HDE #	
Indicate Special Population(s)	 Children  Children who are wards of the state  Adults Unable to Consent  Cognitively Impaired Adults  Neonates of Uncertain Viability  Pregnant Women  Prisoners (or other detained/paroled individuals)  Students/Employees
Sample Size	110
Funding Source	Department of Urology
Indicate the type of consent to be obtained	 Written  Verbal/Waiver of Documentation of Informed Consent  Waiver of HIPAA Authorization  Waiver/Alteration of Consent Process
Site	 Lead Site (For A Multiple Site Research Study)  Data Coordinating Center (DCC)
Research Related Radiation Exposure	 Yes  No
DSMB / DMC / IDMC	 Yes  No

OBJECTIVES:

This study is designed to assess if there is a significant difference in same day discharge rates after Holmium Laser Enucleation of the Prostate (HoLEP). We attempt to perform HoLEP as a same-day discharge (SDD) procedure, but at NM, our SDD rate is currently approximately 60%. The limiting factor in SDD is hematuria. Tranexamic acid (TXA) is a clot promoting drug that is commonly used by orthopedic, cardiac and obstetric surgeons to prevent bleeding. Our

STU#:

primary outcome will be to assess if there is a difference in SDD rates in those who receive TXA vs. those who do not.

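### Do the swapped role words in the group definitions (TXA as control, no TXA as experimental) put the trial's results at risk?

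*Protocol*

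**What the plan says.** The group definitions in Recruitment Methods read "Group 1 (control): Receive intraoperative 1g TXA" and "Group 2 (experimental): No TXA". The paragraph after them says that allocation to Group 1 or Group 2 runs through REDCap, and adds: "The stratified randomization list will be created and provided by the study statistician before the start of patient recruitment".

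The rest of the protocol treats TXA as the intervention:

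- **Title:** "Tranexamic Acid to Improve Same-day Discharge Rates After Holmium Laser Enucleation of the Prostate (HoLEP)".
- **Study Summary:** tranexamic acid is entered as the investigational agent.
- **Objectives, primary outcome:** "primary outcome will be to assess if there is a difference in SDD rates in those who receive TXA vs. those who do not".
- **Objectives, expected effect:** "We anticipate that there may be up to a 25% increase in SDD rates in those who receive TXA vs. those who do not".
- **Background, reference rate:** "Our current SDD rate is approximately 60" per cent.
- **Potential Benefits:** "Patients in the TXA arm may have higher rates of success with same day discharge and same day catheter removal".

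**The concern.** The group definitions are the only place where the randomised arms are set out, and there the role words contradict the rest of the protocol. A statistician building the allocation list, a programmer labelling the arm variable or someone completing a results record would naturally start from this text.

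If any of them worked from the role words and formed experimental minus control, a benefit of TXA on same-day discharge would appear as a harm. The bleeding comparison would reverse in the same way, and thrombotic events and seizures in treated patients would be listed under *control*. In the worst case, someone might match drug to arm by role and treat the wrong group.

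**Working it through.** **1. Is the contradiction real?** Yes. The innocent reading would be that TXA is already routine and the trial tests leaving it out. The Background excludes this: it reports that TXA has not been studied in HoLEP, and it gives the current discharge rate as the figure to improve on. The role words are simply transposed.

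**2. What in the plan depends on the role words?**

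| Step | How the protocol identifies the arms | Uses *control* or *experimental*? |
|---|---|---|
| Allocation | Group 1 or Group 2, in REDCap | No |
| Treatment given | Printed beside each group number | No |
| Patient instruction at Visit 1 | Whether or not TXA is to be received | No |
| Primary contrast | Receives TXA against does not | No |
| Bleeding complications | Receives TXA against does not | No |
| Expected effect | Increase in those who receive TXA | No |
| Expected benefit | The TXA arm | No |

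The map from group number to treatment is unambiguous, and no passage defines an effect as experimental minus control.

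**3. What would happen if someone did code by role?** The inputs are 60% without TXA (the current rate, taken as the no-TXA rate) and an increase of up to 25%. The protocol does not say whether the 25% is absolute or relative, so both readings are shown.

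- Absolute: the TXA rate is 0.60 + 0.25 = 0.85. TXA minus no TXA is +0.25. Experimental minus control, as labelled, is 0.60 − 0.85 = −0.25. The odds ratio is (0.85/0.15)/(0.60/0.40) = 3.78, or 1/3.78 = 0.26 when reversed.
- Relative: the TXA rate is 0.60 × 1.25 = 0.75. The differences are +0.15 and −0.15, and the odds ratios are 2.0 and 0.5.

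Each pair describes one comparison from its two ends. The negative figure is correct for no TXA minus TXA. It misleads only if the treatment name is dropped and the role word stands alone.

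**4. Do power or the test change?** The protocol gives a total of 110 but no alpha, power, allocation ratio or dropout allowance, so the total cannot be strictly reproduced. Assume two-sided 5% and 1:1 allocation, which gives 55 per arm. For rates p1 and p2 with mean p̄ and n per arm,

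power = Φ{ [ |p1 − p2|√n − 1.96√(2p̄(1 − p̄)) ] / √(p1(1 − p1) + p2(1 − p2)) }.

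- 0.60 and 0.85, p̄ = 0.725: (0.25 × 7.416 − 1.96 × 0.6315)/0.6062 = 0.616/0.606 = 1.017, so power is 84.5%.
- 0.60 and 0.75, p̄ = 0.675: (0.15 × 7.416 − 1.96 × 0.6624)/0.6538 = −0.186/0.654 = −0.284, so power is 38.8%.

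The expression is symmetric in p1 and p2, so exchanging the labels leaves both figures as they are. The same symmetry holds for the two-sided p-value and for the sample size: under the absolute reading with 80% power it is 49 per arm, 98 in all, or 98/0.9 = 109 after an assumed 10% dropout.

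**The case for a change.** The strongest case for acting is that the error sits in operative text, is beyond dispute and would cost two words to correct. The safeguards described in the protocol might not catch it. There is no data monitoring committee, data are entered once and spot-checked, and such checks test individual entries rather than the meaning of an arm label. Data are also extracted for analysis every three months during enrolment, so a miscoded arm could recur at each extraction. A one-sided test or a results table arranged by role would be affected.

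Part of this stands. The labels are wrong, and a table headed by role alone could mislead a reader who had not seen the treatment text.

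The rest depends on steps that the plan does not take. It specifies no one-sided test and no contrast by role, and the objective is framed as a difference between treatments. Giving the drug to the wrong group would mean ignoring the treatment stated on the same line as the group number. Thrombotic events and seizures would still be counted among the patients who received TXA, whatever role heading was used. Nothing in the document shows that the role words were carried into the allocation list or the REDCap arm field.

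**Conclusion.** The inconsistency is genuine but clerical. Carried out as written, the protocol sends the same patients to TXA, compares TXA with no TXA, and yields the same estimate, two-sided p-value and power as it would with the role words exchanged. The effect on any planned result is zero. The reversal of 25 points (15 under the relative reading) arises only if someone codes or reports by role word alone, which the plan never asks for.

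This rests on two assumptions: that the allocation list and REDCap arm field, which are not shown, follow the printed map from group number to treatment, and that analyses contrast the arms by treatment, as the Objectives do. Exchanging the two words when the protocol is next edited would be good housekeeping. No change to the design, allocation or analysis follows.
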